11.1.2 Primary Endpoint: Analysis of Neuropsychological Changes

For each neuropsychological test, descriptive statistics will be reported for the measured score at baseline and each follow-up visit. In addition, change from baseline will be calculated at each follow-up visit and descriptive statistics will be reported. For each subject, the change from baseline will be categorized as improved, unchanged, or deteriorated based on whether the change exceeds a pre-specified threshold determined by Reliable Change Index (RCI) methodology for that specific neuropsychological test with a 95% confidence level. The threshold thus represents a degree of change that is unlikely (<2.5% chance in either direction) to occur due to measurement error of the neuropsychological instrument alone. The proportion of subjects in each category at each follow-up time will be tabulated.

For each neuropsychological test, the RCI with 95% confidence level is calculated as $1.96 \times S_{diff}$ where S_{diff} is the standard error of the difference between the baseline and follow-up neuropsychological test score. The standard error of measurement is used to calculate the standard error of the difference.

$$S_{diff} = \sqrt{SEM_1^2 + SEM_2^2}$$

The standard error of measurement is calculated based on the standard deviation of the test score across subjects (SD) and the test-retest reliability (r) of the test with the equation

$$SEM_1 = SD_1 \sqrt{1 - r}$$

In order to approximate S_{diff} for the population of subjects enrolled in the study, the observed standard deviation at baseline (SD1) will be used to calculate both SEM1 and SEM2. The approach assumes that the variation SD2 would be the same as SD1 if all subjects were re-tested at the specified follow-up interval without having undergone treatment with the study device. Since SD2 cannot be observed, it is approximated by SD1. The test-retest reliability for each test is obtained from published literature and will be documented prior to performing analysis. A particular subject's change from baseline in a neuropsychological test score will be considered statistically different from measurement error if the observed difference exceeds $1.96 \times S_{diff}$.

As there is no control group for comparison, any observed changes in neuropsychological function will need to be evaluated in comparison to longitudinal changes observed in prior longitudinal studies of similar subjects, examining typical changes in both subjects that have and have not undergone invasive therapy. In addition, since up to 2.5% of subjects are expected to have a change as large as the RCI in each direction (positive and negative), observed proportions will be interpreted based on the degree to which they differs from 2.5%.

For the primary analysis of neuropsychological changes, English and Spanish language versions of the same test will be considered interchangeable and pooled together for analysis. Sensitivity analyses will be performed by analyzing English and Spanish versions separately.

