LITT Treatment				✓														
MRI					✓	✓								✓				
Surgical pain VAS						✓	✓											
Surgical outcome classifications ³										✓		✓		✓				✓
Subject satisfaction												✓						✓

Abbreviations: C; collect; D; dispense; DC; discharge; I; initial; LITT; laser interstitial thermal therapy; Mo.; month; MRI; magnetic resonance imaging; QOLIE-31; Quality of Life in Epilepsy - 31; U; update; VAS; visual analog scale.

¹ See Appendix A for details of the neuropsychological testing at each visit. These can be performed on a separate day than the study visit, as long as it is completed within the study window.

² Prior neuropsychological testing may be used for baseline values if the testing was conducted within 6 months prior to the specific baseline visit and there were no significant changes to the subject's AEDs or changes to the subject's clinical condition that may affect cognitive function.

³ See Appendix B for details about the Engel and ILAE surgical outcome classifications.

Table 2: Visits and Testing Requirements and Data Collection Summary (Month 13 through Month 24)

	Months 13, 14, 15, 16, & 17	Month 18	Months 19, 20, 21, 22, & 23	Month 24	Early Withdrawal
Visit Window	± 7 days	± 14 days	± 7 days	± 14 days	
Visit Type					
QOLIE-31		✓		✓	✓
Medication review (epilepsy and non-epilepsy)	✓	✓	✓	✓	
Neurological exam		✓		✓	✓
Functional assessment		✓		✓	✓
Seizure diary	C/D	C/D	C/D	C	
Adverse event monitoring	✓	✓	✓	✓	✓
Surgical outcome classifications ¹		✓		✓	✓
Subject satisfaction		✓		✓	✓
Neuropsychological testing ²					✓

Abbreviations: C; collect; D, dispense; QOLIE-31, Quality of Life in Epilepsy - 31; U, update.
¹ See Appendix B for details about the Engel and ILAE surgical outcome classifications.
² See Appendix A for details of the neuropsychological testing.

9 Sample Size

For this feasibility study, there are no hypothesis tests and therefore sample size is not based on power. Rather, the sample size of 30 subjects is based on providing a sufficiently robust characterization of adverse events and other study endpoints. With a sample size of 30 subjects, adverse events that have a 5% probability per-subject have approximately an 80% chance of being observed in at least one subject in the study. Study results obtained from a sample of 30 subjects will permit planning for the potential range of results that could occur in a larger pivotal trial.

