Up to 45 subjects will be enrolled at up to 8 sites in the United States to ensure that approximately 30 subjects undergo the LITT procedure. It is expected that each site will enroll no more than 10 subjects to ensure that all sites have an opportunity to contribute data to the study and to prevent any one site from having an outsized influence on the overall results of the study.

10 Analysis Populations

The following analysis populations are defined:

- **Enrolled Set:** All subjects enrolled in the study
- **Treated Set:** All subjects that received thermal delivery with the NBS
- **Per-protocol Set:** A subset of the Treated Set that does not have a protocol deviation (see below)

In the feasibility study setting, conclusions about performance are best informed by analyses of the Treated Set. Analyses may be repeated on the Enrolled Set for full reporting of study results and on the Per-protocol Set to provide insight into the potential impact of protocol deviations on the analysis results.

The Per-protocol Set will exclude subjects with protocol deviations that seriously affect the integrity of the data. The deviations that will result in subject data being excluded from the Per-Protocol Set are:

1. Subject did not meet the following study inclusion criteria:

- Diagnosis of unilateral medial temporal lobe epilepsy (MTLE) confirmed clinically and with either (1) ictal scalp recording and MRI evidence of mesial temporal sclerosis or (2) intracranial ictal onset consistent with hippocampal origin.
- Subject or legally authorized representative is able to provide appropriate consent to participate.
- Subject averages 3 or more complex partial seizures (with or without secondary generalization) per month over the 3 most recent consecutive months prior to baseline.

2. Subject should not have undergone the study procedure (i.e. subject was found not to have met the treatment eligibility criteria in Section 6.4 of the clinical study protocol)

Protocol deviations may be reviewed prior to performing analysis of study outcomes to identify deviations, in addition to those identified above, that may result in excluding a subject from the per-protocol set. Reviewing protocol deviations prior to analysis of outcomes is intended to prevent bias in the analysis results while still allowing for identification of significant protocol deviations that could impact outcomes but that were not anticipated at the time that the Statistical Analysis Plan was written.

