15.3 CEC Adjudication

In all tabulations of adverse events, the categorizations of adverse events determined by the CEC (e.g. relatedness of adverse events to the device treatment or procedure) will be reported, if available, and categorizations provided by investigators will be reported otherwise. Adverse event listings will report both CEC and investigator categorizations.

16 Interim Analyses

Analyses will be reported on data from baseline through a major study time point once all subjects have completed that major study time point (e.g., 6 months, 12 months and 24 months). There is minimal opportunity for bias since all procedures will have been completed before any analysis is reported and all data will have been collected for a time point before analysis of that time point is reported.

The study's DSMB may request descriptive analyses of accumulating data at its discretion.

17 Missing Data Analyses

Every effort will be made to reduce the incidence of missing data. The study will be conducted with proper screening of study subjects, complete training of participating investigators, study coordinators and monitors. All subject data that are available on subjects who drop out during the study will be included.

The number and proportion of subjects eligible for and compliant with each follow-up examination will be presented. Subjects who withdraw from the study will be tabulated with reasons for withdrawal. Sensitivity analyses, such as multiple imputation or worst case imputation, may be performed to assess the robustness of study conclusions to the potential impact of missing data.

In worst case imputation, for binary endpoints the worse of the two possible outcomes will be imputed. The timing of the imputed event will be the last known event-free date for subjects that exit the study prematurely. For continuous endpoints assessed at a single time period (e.g. quality of life), the worst observed value among subjects with observed data at that time period will be imputed for subjects with missing data. For rates corresponding to a specific follow-up time interval, any partial observed data for a subject will be used. Data for the missing portion of the subject's follow-up time interval will be imputed using the worst observed value among all subjects with observed data during the corresponding missing portion of the follow-up time interval, in order to calculate an imputed rate for the overall follow-up time interval.

18 Sensitivity Analyses

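### The reliable-change proportions have no stated denominator and no rule for a subject whose deficit prevents testing, so cognitive decline can be understated in that part of the primary safety endpoint

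*SAP*

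**What the plan says.** The primary endpoint is safety, with two components: adverse events and neuropsychological change (SAP 7).

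For the second component, SAP 11.1.2 states that "the change from baseline will be categorized as improved, unchanged, or deteriorated". The rule compares the observed difference from baseline with 1.96 × Sdiff. Then "The proportion of subjects in each category at each follow-up time will be tabulated". The results are read against a chance rate in each direction: "observed proportions will be interpreted based on the degree to which they differs from 2.5" per cent.

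SAP 11.1.2 does not say which subjects form the denominator. Other sections do: SAP 11.1.1 uses enrolled subjects for adverse events, and SAP 11.1.3 uses subjects completing the visit for Engel and ILAE class. SAP 10 says that "conclusions about performance are best informed by analyses of the Treated Set", but nothing ties the reliable-change table to that set.

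The core battery is scheduled at baseline, Month 12 and Early Withdrawal only (Protocol Appendix C, Tables 5 and 6; SAP Appendix A). The supplementary battery, for English speakers only, is given at baseline and Months 3, 6 and 12.

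On missing data, SAP 17 says "Subjects who withdraw from the study will be tabulated with reasons for withdrawal" and "Sensitivity analyses, such as multiple imputation or worst case imputation, may be performed". It also says that available data on dropouts will be included. Its worst-case method covers binary and continuous endpoints and does not mention the neuropsychological categories.

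**The concern.** A category exists only where there is a score. The core tests call for naming, word production, timed tracing and peg placement, and Protocol 11.1 lists aphasia, hemiparesis, coma and loss of mental function among the possible risks. A subject with a severe enough deficit may be unable to complete a test. Trail Making shows the problem most plainly: its main measure is time to completion, and the documents do not say how a non-completion is scored.

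For such a subject the harm being measured is also the reason that the score is missing. Because the core battery has one scheduled post-procedure assessment before withdrawal, no other scheduled core score can stand in. The table for that test would then describe only those well enough to take it, in a component of the primary safety endpoint that is reported and interpreted separately. SAP 19 also compares these proportions by site, where one subject weighs more.

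**Working it through.** **Inputs from the documents.** Sample size 30 and the 5% / 80% statement (SAP 9); reference rate 2.5% in each direction (SAP 11.1.2); Clopper-Pearson intervals for proportions (SAP 12.1); about 20% reliable decline in verbal memory after non-dominant lobectomy (Protocol Appendix C).

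**Assumptions.** The documents give no rate of untestability or dropout, so one or two untestable subjects, and three or five unscored subjects for any reason, are illustrations. The 20% is borrowed as a plausible level of decline; it is not a LITT figure.

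**1. The plan's own figure.** SAP 9 says that "adverse events that have a 5% probability per-subject have approximately an 80% chance of being observed in at least one subject". 1 − 0.95^30 = 0.785, which agrees with the stated 80%.

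**2. Weight of one subject.** 1/30 = 3.3 percentage points, more than the 2.5% reference. Including or dropping one subject can therefore decide whether a test shows no decline or a proportion above the reference.

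**3. Untestable subjects, no other decline.**

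| Untestable because of deficit | Observed scores only (95% CI) | Counted as deteriorated (95% CI) |
|---|---|---|
| 1 | 0/29 = 0% (0 to 11.9%) | 1/30 = 3.3% (0.1 to 17.2%) |
| 2 | 0/28 = 0% (0 to 12.3%) | 2/30 = 6.7% (0.8 to 22.1%) |

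**4. Does the SAP 17 worst-case rule close the gap?** It depends on how the rule is applied.
- To the change score: the worst value among tested subjects is imputed. If none of the 29 crossed the threshold for decline, that value has not crossed it either, and the untestable subject is classed as unchanged.
- To the raw follow-up score: the lowest observed score is imputed, and the category then depends on the subject's own baseline.
- To deteriorated yes/no as a binary outcome: the subject is classed as deteriorated.

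The SAP does not choose among these, and the analysis is optional.

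**5. Direction of the error.** Suppose that 6 of 30 truly declined (20.0%), m subjects are unscored and k of those m are decliners. The observed-score rate is (6 − k)/(30 − m).
- m = 3: from 3/27 = 11.1% (k = 3) to 6/27 = 22.2% (k = 0).
- m = 5: from 1/25 = 4.0% (k = 5) to 6/25 = 24.0% (k = 0); at k = 1 it is 5/25 = 20.0%, with no error.

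The rate is understated only when k/m exceeds 6/30, that is, when unscored subjects declined more often than the whole group.

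**6. Effect of the denominator alone.** With 6 observed decliners and 3 unscored for unrelated reasons, moving to all treated takes 6/27 = 22.2% to 6/30 = 20.0%. An all-treated denominator can lower the rate as well as raise it.

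**The case against.** A reader might infer that subjects who die, withdraw or become severely impaired leave the primary safety analysis altogether, and that decline is therefore understated. The documents do not support that, for four reasons.

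- **Adverse events.** Their rates use all enrolled subjects (SAP 11.1.1), and death and permanent impairment of function meet the SAE definition (Protocol 9.1). Only the reliable-change tables are exposed.
- **Withdrawals.** These subjects are not all unscored. The core battery is scheduled at Early Withdrawal, and available dropout data are to be included. English speakers who leave after Month 3 already have supplementary scores. What is undefined is where Early Withdrawal scores go. That visit is also not imperative after withdrawal of consent or loss to follow-up (Protocol 7.8).
- **Aphasia.** It need not mean a missing score. Few correct names or words on the naming and fluency tests is a low score, likely to be classed as deteriorated. True untestability is narrower, and its rate is unknown.
- **Direction.** Protocol 7.8 lists subject request and loss to follow-up among the withdrawal reasons, and these need not be linked to cognition. Step 5 shows that the error can run either way.

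It can also be said that the study is descriptive, has no hypothesis tests, and will be read against earlier longitudinal studies as well as 2.5%. That limits the consequence. Nor is the 2.5% reference defined for assigned categories, which is a fair reason to keep the observed-score result visible. None of this supplies the missing denominator or a rule for the subject who cannot be tested.

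**Conclusion.** The point holds in a limited form. Within the neuropsychological component, SAP 11.1.2 leaves the denominator open and drops a subject from a test's proportion when a deficit prevents completion. For those subjects the missing score is linked to the outcome, so decline can be understated. The stronger conclusion, that decline will be understated or that the primary safety denominator as a whole is affected, is not supported.

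The size is 3.3 percentage points per untestable subject at 30 treated. That is small in absolute terms but larger than the 2.5% reference. It rests on the assumption that at least one treated subject is untestable for this reason. SAP 9 says that "the sample size of 30 subjects is based on providing a sufficiently robust characterization of adverse events and other study endpoints"; with so few subjects, how each one is counted should be settled beforehand. This is worth correcting in the SAP before analysis; it does not undermine the design.

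**What to change.** In SAP 11.1.2:

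1. State the denominator for each test as treated subjects with a valid baseline on that test. Beside each proportion, show the number unscored by reason: unable because of a neurological or cognitive deficit, death, withdrawn, other.
2. Make mandatory a pre-specified analysis in which a test not completed because of a neurological or cognitive deficit counts as *deteriorated*, reported next to the observed-score result. The latter stays available for comparison with earlier studies.
3. Report Early Withdrawal core-battery categories in a separate flagged row and do not substitute them for Month 12. Protocol Appendix C notes that early word-retrieval deficits resolve to varying degrees, so an early score may not represent Month 12.

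The cost is SAP wording and, if the neuropsychological case report form does not already record why a test was not done, one reason code; the forms are not among the documents. The SAP cites Protocol Rev A while the protocol is at Rev B, so it needs revisiting anyway. The downside is that a few categories are assigned rather than measured, and the reported rate may move in either direction depending on how the other missing subjects are shown.

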Boston Naming Test-60 (BNT-60)

The 60-item BNT is a visual confrontation naming test sensitive to deficits in semantic retrieval. The BNT contains 60 line drawings graded in difficulty. Subjects are required to verbally name pictures (line drawings) of common objects. Items are rank ordered in terms of their ability to be named, which is correlated with their frequency. This test is appropriate for adults.

Controlled Oral Word Association Test (COWAT)

The COWAT uses the three letter set of F, A, and S to assess phonemic fluency. Individuals are given 1 minute to name as many words as possible beginning with one of the letters. The procedure is then repeated for the remaining two letters.

Animal Naming Test

The animal naming test is a category fluency test that measures impairment in verbal production, semantic memory and language. The subject is asked to verbally name as many animals as they can in a 60 second time period.

Trail Making Test

The test consists of two parts and requires a subject to 'connect-the-dots' of 25 consecutive targets on a sheet of paper or computer screen as fast as possible while still maintaining accuracy. If the subject makes an error, the test administrator is to correct them before the subject moves on to the next dot. The goal of the test is for the subject is to finish the part A and part B as quickly as possible. The time taken to complete the test is used as the primary performance metric. Part A is used primarily to examine cognitive processing speed. Part B is used to examine executive functioning.

Grooved Pegboard Test

The Grooved Pegboard is a manipulative dexterity test. This unit consists of 25 holes with randomly positioned slots. Pegs, which have a key along one side, must be rotated to match the hole before the peg can be inserted. This test requires more complex visual-motor coordination than most pegboards. Completion time is estimated at 20 minutes.

Supplementary Battery – English-Speaking Subjects Only

Logical Memory Test

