Raven's SPM is a test commonly used as a nonverbal means to estimate intelligence level in non-English speaking subjects. It will be used as an IQ estimate for Spanish-speaking subjects participating in this study. The test assesses observation skills and clear-thinking ability. It offers insight about someone's capacity to observe, solve problems, and learn. The test has a total of 60 items presented in 5 sets (A–E), with 12 items per set. The Raven's SPM produces a single raw score as well as percentile rank to indicate

¹⁹ Hamberger MJ, Seidel WT. Auditory and visual naming tests: normative and patient data for accuracy, response time, and tip-of-the-tongue. *J Int Neuropsychol Soc*. 2003;9(3):479-489.

the candidate's educative ability or the ability to think clearly and extract meaning out of events, compared to a norm group.

WHO-UCLA Auditory Verbal Learning Test (AVLT)

This is version of the RAVLT paradigm modified for non-English-speaking subjects. The Spanish translation will be used for Spanish-speaking subjects participating in this study. Like the RAVLT, it is a verbal learning and memory test that consisting of a list of 15 different words, which an examiner reads aloud at the rate of one per second. The subject's task is to repeat all the words he or she can remember, in any order. This procedure is carried out a total of five times. Then the examiner presents a second list of 15 words, allowing the subject only one attempt at recall. Immediately following this, the subject is asked to remember as many words as possible from the first list. This is followed by a yes/no recognition trial, where subjects are asked to distinguish the 15 original words from 15 distractor words. Completion time is estimated at 15 minutes.

Ponton-Satz Boston Naming Test (PS-BNT)

The PS-BNT is a modified version of the Boston Naming Test consisting of 30 items from the original BNT selected by experts on the basis of appropriateness for the use with Spanish speakers. As in the English version, subjects are required to verbally name pictures (line drawings) of common objects. Items are rank ordered in terms of their ability to be named, which is correlated with their frequency.

Controlled Oral Word Association Test (COWAT)

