APPENDIX A NEUROPSYCHOLOGICAL TESTING

This study will include a core neuropsychological battery as well as a supplementary battery, which are described in detail in the study protocol and listed in the tables below. The tests differ based on a subject's spoken language.

Table 3: Neuropsychological Testing Requirements for English-Speaking Subjects

Test	Baseline Week -12	Baseline Week -4	Month 3	Month 6	Month 12	Early Withdrawal
CORE						
WAIS-IV	X				X	X
RAVLT		X			X	X
BNT-60		X			X	X
COWAT		X			X	X
Animal Naming		X			X	X
Trail Making		X			X	X
Grooved Pegboard		X			X	X
Supplementary						
Logical Memory		Form 1	Form 2	Form 3	Form 1	
Auditory Naming		Form 1	Form 2	Form 3	Form 1	
Visual Naming		Form 1	Form 2	Form 3	Form 1	
Verbal Fluency		Form 1	Form 2	Form 3	Form 1	

Table 4: Neuropsychological Testing Requirements for Spanish-Speaking Subjects

Test	Baseline Week -12	Baseline Week -4	Month 3	Month 6	Month 12	Early Withdrawal
Core						
Raven's Matrices	X				X	X
WHO-UCLA AVLT		X			X	X
Ponton-Satz BNT		X			X	X
COWAT		X			X	X
Animal Naming		X			X	X
Color Trails		X			X	X
Grooved Pegs		X			X	X

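### Pooling the 60-item English and 30-item Spanish naming tests under one baseline SD usually makes the naming Reliable Change threshold too wide, so fewer declines are flagged

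*SAP*

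**What the plan says.** SAP 11.1.2 classifies each subject's change on each test as improved, unchanged or deteriorated. The threshold is 1.96 × S_diff, with S_diff = √(SEM1² + SEM2²) and SEM = SD√(1 − r). The reliability r comes from the literature. The SD comes from the study: "the observed standard deviation at baseline (SD1) will be used to calculate both SEM1 and SEM2". On the scale of the scores, the section says only that "descriptive statistics will be reported for the measured score at baseline and each follow-up visit".

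On language, it says for the primary analysis that "English and Spanish language versions of the same test will be considered interchangeable and pooled together for analysis". It adds: "Sensitivity analyses will be performed by analyzing English and Spanish versions separately". On interpretation, it says that "observed proportions will be interpreted based on the degree to which they differs from 2.5" percent.

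Protocol Appendix C describes the two naming tests. Of the English test: "The BNT contains 60 line drawings graded in difficulty". Of the Spanish test: "The PS-BNT is a modified version of the Boston Naming Test consisting of 30 items from the original BNT". Protocol 6.3.1, inclusion criterion 12, admits Spanish speakers. Neither document says how many are expected.

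**The concern.** Appendix C presents the Spanish naming test as a version of the English one, so the pair falls under the pooling rule. One scale runs from 0 to 60 and the other from 0 to 30. An SD taken across both contains the difference in test length, which is not measurement error. Pooled naming means and mean changes would also mix the scales.

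A threshold that is too wide still meets the SAP's literal promise that chance exceedance is below 2.5% in each direction. Two things are lost: the calibration to 2.5% against which the observed proportions are to be read, and the ability to flag decline. The proportion deteriorated on naming is part of the primary safety endpoint, so the error mostly runs toward missing harm. The same classifications feed the between-site comparison of each core test in SAP section 19.

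**Working it through.** **Inputs from the documents.** 30 treated subjects; 60 and 30 items; multiplier 1.96; one observed baseline SD per test.

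**Inputs assumed.** The documents give no naming means, SDs, r or Spanish share. I took r = 0.90, with 1 or 5 Spanish speakers in 30, and nine pairs of score distributions.

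**The plan's own figure.** 1 − Φ(1.96) = 2.5% per direction. This reproduces when the SD is that of the version the subject took.

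**Formulas.** Subscripts E and S are the language groups and gap is the difference in means.

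- Expected pooled variance = (nE·sE² + nS·sS²)/n + [nE·nS/(n(n − 1))]·gap². With n = 30 the gap coefficient is 29×1/870 = 0.033 with 1 Spanish speaker and 25×5/870 = 0.144 with 5.
- Threshold = 1.96 × √(2(1 − r)) × SD.
- Ratio = pooled SD / version SD.
- False-flag rate per direction = 1 − Φ(1.96 × ratio). It does not depend on r.
- Probability of flagging a true loss of L version-SDs = Φ(L/√(2(1 − r)) − 1.96 × ratio). At r = 0.90, L = 1.1 and ratio 1 this is Φ(2.46 − 1.96) = 69%.

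**Scenario A, 1 Spanish speaker.** Within-version variance = (29×64 + 1×16)/30 = 62.4. Gap part = 0.0333×24² = 19.2. Pooled SD = √81.6 = 9.03. Threshold = 1.96×0.447×9.03 = 7.9 points, against 7.0 (SD 8) and 3.5 (SD 4). Ratios are 9.03/8 = 1.13 and 9.03/4 = 2.26. Flagging of a 1.1-SD loss falls to 60% (English) and 2.5% (Spanish).

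**All scenarios.** Each cell gives English / Spanish. The reference values are 2.5% false flags and 69% flagged.

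| Scenario: English v Spanish, mean/SD | Ratio, 1 Sp. | False flags %, 1 Sp. | 1.1-SD loss flagged %, 1 Sp. | Ratio, 5 Sp. | False flags %, 5 Sp. | 1.1-SD loss flagged %, 5 Sp. |
|---|---|---|---|---|---|---|
| A 46/8 v 22/4 | 1.13 / 2.26 | 1.3 / <0.01 | 60 / 2.5 | 1.47 / 2.94 | 0.2 / <0.01 | 33 / <0.1 |
| B 50/6 v 24/4 | 1.27 / 1.90 | 0.6 / 0.01 | 49 / 10 | 1.90 / 2.85 | 0.01 / <0.01 | 10 / 0.1 |
| C 42/9 v 20/5 | 1.08 / 1.95 | 1.7 / <0.01 | 63 / 9 | 1.32 / 2.38 | 0.5 / <0.01 | 45 / 1.4 |
| D 36/10 v 22/5 | 1.02 / 2.04 | 2.3 / <0.01 | 68 / 6 | 1.08 / 2.15 | 1.8 / <0.01 | 64 / 4 |
| E 36/12 v 27/3 | 0.99 / 3.97 | 2.6 / <0.01 | 70 / 0 | 0.96 / 3.85 | 3.0 / <0.01 | 72 / 0 |
| F 46/8 v 22/6 | 1.13 / 1.51 | 1.3 / 0.15 | 59 / 31 | 1.49 / 1.99 | 0.2 / <0.01 | 32 / 8 |
| G 46/8 v 22/8 | 1.14 / 1.14 | 1.3 / 1.3 | 59 / 59 | 1.51 / 1.51 | 0.15 / 0.15 | 31 / 31 |
| H 36/10 v 22/8 | 1.03 / 1.28 | 2.2 / 0.6 | 67 / 48 | 1.11 / 1.38 | 1.5 / 0.3 | 61 / 40 |
| I 36/8 v 26/8 | 1.03 / 1.03 | 2.2 / 2.2 | 67 / 67 | 1.11 / 1.11 | 1.5 / 1.5 | 61 / 61 |

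**Larger loss.** A true 2-SD loss is flagged 99% of the time with the right threshold. For Spanish speakers under pooling, with 1 enrolled, it is flagged 52–77% of the time in A–D, about 0% in E and 93–99% in F–I. With 5 enrolled the figures are A 10%, B 13%, C 43%, D 60%, E about 0% and F–I 72–99%. For English speakers it is 98–99% with 1 and 77–99.5% with 5.

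**Why usually and not always.** From the variance formula, the pooled SD exceeds the English SD when gap² > [(n − 1)/nE]·(sE² − sS²). With one Spanish speaker that is gap > √(sE² − sS²). Scenario E fails this: √(144 − 9) = 11.6 against a gap of 9. Over 4,950 combinations (English mean 36–56 and SD 4–12; Spanish 50–90% correct and SD 2–6; 1–10 Spanish speakers) the pooled SD exceeded the English SD in 99%. When the Spanish SD is no larger than the English SD and the means differ, the pooled SD always exceeds the Spanish SD.

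**Sensitivity to r.** At r = 0.80 the right threshold flags a 1.1-SD loss 41% of the time. Scenario A with one Spanish speaker gives 32% (English) and 0.4% (Spanish).

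**Normed scores.** T-scores of 45/10 for English against 45/10, 40/10, 45/8 or 38/9 for Spanish (1, 3 or 5 Spanish speakers) give Spanish false flags of 0.7–2.5% and 51–69% flagged for a 1.1-SD loss. English figures are 2.3–2.9% and 68–71%. Most of the problem disappears.

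**The case against.** The strongest reply is that one threshold per instrument is meant. SAP 11.1.2 ties the threshold to the specific test and takes r test by test. SAP Appendix A lists the two naming tests in separate tables and says "The tests differ based on a subject's spoken language". Pooling could then mean only that classified subjects are counted together. The SAP also never says that naming is analysed raw. This reading is possible, but the SAP does not state it for the primary analysis. The section points the other way by leaving separate analysis of the versions to sensitivity analyses. Two readings that give different primary tables need to be settled before analysis.

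Second, the separate-language analysis is a firm commitment and would give a sound English naming table. That is true, but the primary table stays uncorrected. The Spanish table would also be weak: an SD cannot be computed from one subject and is unstable from a few.

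Third, every score input is assumed and the results run from nothing to near-total loss. They show what can happen, not what is likely. That stands.

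Fourth, lost calibration is hard to see at this size. Expected false flags per direction are 30 × 0.025 = 0.75 subjects, and none at all occur with probability 0.975³⁰ = 47%. In scenario A with one Spanish speaker the expectation falls only to 29 × 0.0134 = 0.39. That also stands, so missed decline is the more serious consequence.

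Finally, English speakers also take auditory and visual naming tests in the supplementary battery, which the pooling does not touch. Spanish speakers do not take that battery.

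**Conclusion.** The concern holds. Followed as written, with raw naming scores, SAP 11.1.2 puts the scale gap into the SD and usually widens the naming threshold. The loss is greatest for Spanish speakers: a 1.1-SD loss that should be flagged 69% of the time is flagged 0–67% of the time with one Spanish speaker enrolled. For English speakers the figure is 49–70% with one Spanish speaker and 10–72% with five. These ranges rest on assumed means, SDs and r = 0.90.

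There is no effect if no Spanish speaker enrols and little if normed scores are used. The point covers naming only, one of seven core tests; the documents show no such scale gap for the other pairs treated as versions of one test. The study is descriptive and no decision rule uses this proportion. It should be fixed, but it sits at the low end of that category.

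**What to change.** Amend SAP 11.1.2 in one paragraph:

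- State the score metric for each test and name the pairs treated as versions of one test.
- In the primary analysis, either classify each subject against a threshold specific to the naming instrument taken, or convert both versions to a stated normed metric before computing the SD.
- Pool only the improved, unchanged and deteriorated categories, and report raw naming means by version.
- With instrument-specific thresholds, do not estimate the Spanish SD from the few Spanish speakers enrolled. Use a published SD for that version and record it, with its r, before analysis.

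The reason for the last item is that an SD estimated from k subjects gives a false-flag rate of about the upper tail of t with k − 1 df at 1.96: 15.0% for k = 2, 9.5% for 3 and 5.4% for 6. For 25 to 29 subjects it is 3.1% to 3.0%, so the English SD can still come from the study.

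The cost is the paragraph plus a published SD and r for the Spanish test, or norms for both versions. A published SD departs from the SAP's aim of approximating S_diff in the enrolled population, and the SAP should say so. If that SD is 20% too low or too high for these subjects, the Spanish false-flag rate becomes 1 − Φ(1.57) = 5.8% or 1 − Φ(2.35) = 0.9%. The normed route avoids that departure but leaves a small mismatch if the two groups' normed SDs differ.
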